## 1.3 Schedule of Activities (SoA)

Table 1-1. Schedule of Activities

Study Activity	Screening	C1 Treatment Period DLT Window (Days 1-21)										Treatment Period (3-week cycles)								UNS Visit a	EOT b	SFU n	Survival FU/LTFU o				
		W1					W2 d			W3		C2		C3			C4 & C5		C6		C7+						
		D1	D2	D3	D5	D6	D7	D8	D9	D10	D15	D1	D15	D1	D8	D15	D1	D1	D2	D15	D1						
Study Day	Day -28 to Day -1																					Within 30d after last dose	90d after last dose	Every 6 months			
Window				±1h	±1h	±1d	±1h	±1h	±1d	±1h	±1h	±1d	±1d	±1d	±1d	±1d	±1d	±1d	±1d	±1d							
Informed Consent	X																					+7d	±7d				
Incl/Excl Criteria	X	X																									
Inpatient Stay c		X	X	X	X c	X c	X c	X c	X c	X c																	
Demographics, Medical & Cancer History, Height	X																										
Complete Physical Exam	X																					X	X				
Symptom-directed Physical Exam		X	X	X	X	X i	X i	X	X k	X k	X	X	X	X	X	X	X	X	X	X	X	X	X				
Weight	X	X																									
Vital Signs d	X	X	X	X	X	X i	X i	X	X k	X k	X	X	X	X	X	X	X	X	X	X	X	X	X	X			
ECHO	X																										
12-Lead ECG	X																										
ECOG Performance Status	X	X																				X	X	X	X		
Clinical Chemistry and Hematology e	X	X	X	X	X	X i	X i	X	X k	X k	X	X	X	X	X	X	X	X	X	X	X	X	X	X			
Coagulation Panel e	X																										
Urinalysis	X																										
Viral Screen	X																										
Testosterone	X																										
AMG 340 administration f		X		X		X j						X	X	X	X	X	X	X	X	X	X						
Anti-AMG 340 antibody e																											

Refer to

Study Activity	Screening	C1 Treatment Period DLT Window (Days 1-21)										Treatment Period (3-week cycles)							UNS Visit a	EOT b	SFU n	Survival FU/LTFU o			
												C2			C3			C4 & C5							
		W1			W2 d			W3			W1	W3	W1	W2	W3	W1	W1	W3	W1	Within 30d after last dose	90d after last dose	Every 6 months			
Study Day	Day -28 to Day -1	D1	D2	D3	D5	D6	D7	D8	D9	D10	D15	D1	D15	D1	D8	D15	D1	D1	D2	D15	D1	UNS Visit a	EOT b	SFU n	Survival FU/LTFU o

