f AMG 340 will be administered intravenously by continuous infusion pump over 120 minutes (± 10 minutes) unless otherwise noted in Section 6.1 of the protocol.

g CCI

h Samples will be collected for disease response as indicated in Table 1-3. Subjects off-treatment for reasons other than disease progression or withdrawal of consent should continue with disease response assessments as described in Table 1-3, until documented disease progression, initiation of subsequent anticancer therapy, or withdrawal (see Table 1-3).

i **C1D6 and C1D7 assessments will only be performed if a priming dose has been implemented on C1D5.**

j A dose will only be administered on C1D8 if a priming dose has been implemented.

k C1D9 and C1D10 assessments will only be performed if a priming dose has been implemented on C1D8.

l All adverse events observed by the investigator or reported by the subject that occur from the time of consent through the safety follow-up visit 90 (+ 7) days after the last dose of study drug should be reported. For subjects that start a new line of therapy before the 90 (+ 7) day follow-up visit, all adverse events should be collected and reported through 30 days post last dose of investigational product/protocol-required therapies or until the subject begins a new line of therapy, whichever occurs later (please refer to Section 8.1.3).

m All serious adverse events observed by the investigator or reported by the subject that occur from the time of consent through the safety follow-up visit 90 (+ 7) days after the last dose of study drug should be reported. For subjects that start a new line of therapy before the 90 (+ 7) day follow-up visit, all serious adverse events should be collected and reported through 30 days post last dose of investigational product/protocol-required therapies or until the subject begins a new line of therapy, whichever occurs later (please refer to Section 8.1.3). During the survival (long-term) follow-up phase, serious adverse events (regardless of causality) that the investigator becomes aware of will be reported to Amgen. After end of study, serious adverse events suspected to be related to investigational product should be reported to Amgen. Please refer to Section 8.4.6.1.3.

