## **6.2 Dose Modification**

### **6.2.1 Dose-cohort Study Escalation/De-escalation and Stopping Rules**

#### **6.2.1.1 Dose Escalation and Selection of the MTD/RP2D Dose**

DLT criteria (see Section [6.2.1.4.1](#)) will be used to make decisions regarding dose escalation. Dose escalation decisions will be based on clinically significant toxicity, DLT events and clinical pharmacology findings, and will be made by the DLRT. A simple majority of the DLRT is required to proceed with dose escalation; for quorum requirements, see Section [11.3](#).

Dose escalation will be based on the BOPN escalation/de-escalation criteria described above (and as illustrated in Yuan et al, 2016; [Figure 1-2](#)), with a target toxicity rate of 30% ( $\lambda_e$  of 0.236 and a  $\lambda_d$  of 0.358). The MTD will be identified via isotonic regression of pooled escalation cohort data ([Table 4-1](#)), according to the BOPN method (Yuan et al, 2016). An expansion dose (eg, RP2D) may be selected by the DLRT prior to the identification of the MTD based on an assessment of available safety, PK/PD, and activity data; in this case the DLRT will also decide whether dose escalation in Part A should continue in parallel. Additional priming doses and intermediate dose levels may

be investigated based on emerging safety, PK, PD, and efficacy data to identify the minimum safe and biologically effective dose (MSBED) [REDACTED]

When the DLRT completes their safety review of cycle 1 for a Cohort N (where N represents a Cohort number), and if that dose is deemed safe (eg, the DLRT endorses further dose escalation or the dose for Cohort N is determined to be the RP2D), any subjects that remain on study at a lower dose of AMG 340 may subsequently be treated at the dose assigned to Cohort N (eg, when the DLRT review for Cohort 5 is complete and the decision to escalate to Cohort 6 has been made, any subjects still on study from Cohorts 1 to 4 may have their dose increased to the dose corresponding to Cohort 5). Subject eligibility for such an escalation must be approved by the Medical Monitor(s) and treating investigator and will be determined on a case-by-case basis. At a minimum, to be eligible subjects must have previously received at least 2 cycles of AMG 340 at their current dose without any drug related toxicities that led to a dose reduction.

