#### **6.2.1.2 Dose Priming**

Based on the nonclinical pharmacology of AMG 340, a lower rate of CRS is anticipated than with other T-cell-engaging bispecifics; however, based on the mechanism of action of AMG 340, the most likely DLT to occur is still CRS  $\geq$  grade 3. Cytokine release syndrome will be managed per Principal Investigator discretion and institutional guidelines (a guide for management of CRS is provided in [Table 6-6](#) if institutional guidelines have not been established). Definitions for adverse events, serious adverse events, and DLTs are provided in Section [8.4.6.1.1](#), [8.4.6.1.2](#), and [6.2.1.4.1](#), respectively.

If a grade  $\geq$  3 CRS event occurs in Cohort N (where N represents a Cohort number) during the DLT period, or at the discretion of the DLRT, a dose equal to or less than the dose for Cohort N will be designated as the ‘Priming Dose’ and dose administration in subsequent cohorts (Cohorts N+1 and on) may be modified as follows:

- On Cycle 1 Day 1, subjects will receive the Priming Dose.
- On Cycle 1 Day 8, subjects will receive the full dose corresponding to the cohort in which they have been enrolled.

Note: a second priming dose may be introduced based on emerging data.

If a subject experiences CRS grade  $\geq$  2, or any other grade  $\geq$  2 toxicity after receiving a priming dose that is not unequivocally due to the subject’s underlying malignancy or other extraneous cause, administration of the full dose on cycle 1 day 8 must await approval by the Amgen Medical Monitor(s). At a minimum, CRS must have resolved to

grade  $\leq$  1 before the next is administered. The dose and timing of the full dose for such a subject may be modified at the discretion of the Amgen Medical Monitor and the Investigator; if the subject has their full dose reduced in cycle 1, the subject will be considered DLT-unevaluable and should be replaced. In subsequent cycles, subjects will receive the full dose on day 1.

Following implementation of a priming dose, if administration of the full dose is delayed in cycle 1, the DLT period for that subject should be extended to the same degree (eg, if the full dose is delayed by 4 days, the DLT period will also be extended 4 days). For clarity, treatment-emergent adverse events meeting criteria for a DLT will be treated as a DLT whether they occur after administration of the priming or the full dose.

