#### **6.2.1.4.1 Dose Limiting Toxicity Definition for Dose Escalation**

The DLT observation period for dose escalation purposes is 21 days and covers the first complete treatment cycle of AMG 340 (1 dose of AMG 340; or up to 3 doses if priming has been implemented). Regular teleconferences will be conducted among the DLRT to examine/confirm potential DLTs, assess adverse events, and evaluate laboratory abnormalities. Events occurring outside the DLT window may be evaluated during these calls when making dose escalation decisions. A DLT is defined as a treatment emergent adverse event that is not unequivocally due to the subject's underlying malignancy or other extraneous cause and meets the criteria below.

The NCI-CTCAE version 5.0 will be used. DLT definitions are provided below.

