#### **8.1.2 Treatment Period**

Visits will occur per the Schedule of Activities (Section 1.3). On-study visits may be completed within the deviation window presented in the Schedule of Activities (Section 1.3). The date of the first dose of AMG 340 is defined as day 1. All subsequent doses and study visits will be scheduled based on the day 1 date. Administration of AMG 340 is to be administered last during each visit that it is required.

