5.1 Study Endpoints

5.1.1 Primary Endpoints Definitions

Treatment-Emergent Adverse Event (TEAE):

Events categorized as Adverse Events (AEs) starting on or after the first dose of AMG 340 as determined by “Did event start before first dose of AMG 340” equal to “No” or missing on the **Adverse Events** eCRF and up to and including 90 days after the last dose of AMG 340 (however, if subject start a new line of therapy before 90 days follow-up visit, safety follow-up will be performed through 30 days post last dose of AMG 340 or until subject begins a new line of therapy, whichever occurs later) excluding events reported after End of Study Date. **Events that are directly related to metastatic castrate-resistant prostate carcinoma cancer or disease progression (including, but not limited to, preferred terms “prostate cancer”, “progression of prostate cancer”, “prostate cancer metastatic”, “disease progression” etc.) will be excluded from TEAE analysis.**

Treatment-Related Adverse Event (TRAЕ):

A treatment-related AE is any treatment-emergent AE with the relationship flag on the **Adverse Events** eCRF indicating there is a reasonable possibility that the event may have been caused by AMG 340. In the unlikely event that the relationship is missing, the treatment-emergent event will be considered treatment-related and documented in a footnote of the treatment-related summary.

Dose-limiting Toxicities (DLTs):

Investigators determine whether a TEAE qualifies as a DLT per the definition described in protocol section 6.2.1.4.1. For an adverse event to qualify as DLT, the start date must be within 21 days from the date of first dose of AMG 340.

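### In primed cohorts the full dose is observed for 14 days rather than 21, the SAP drops DLTs that the protocol's delay extension counts, and footnote k calls the Day 8 dose a priming dose

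*Protocol*

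**What the plan says.** Protocol 6.2.1.4.1 sets a single window for every cohort: "The DLT observation period for dose escalation purposes is 21 days and covers the first complete treatment cycle of AMG 340". It notes that the cycle may hold one dose, or up to three with priming. The Schedule of Activities (Table 1-1) heads the same span "C1 Treatment Period DLT Window (Days 1-21", and Protocol 8.1.2 fixes the origin: "The date of the first dose of AMG 340 is defined as day 1".

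Protocol 6.2.1.2 places the doses in primed cohorts: "On Cycle 1 Day 1, subjects will receive the Priming Dose", then "On Cycle 1 Day 8, subjects will receive the full dose corresponding to the cohort in which they have been enrolled". It adds two rules. If the full dose is late in cycle 1, the subject's DLT period lengthens by the same number of days. Qualifying events count as DLTs whether they follow the priming dose or the full dose.

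SAP 5.1.1 has only a first-dose rule: "the start date must be within 21 days from the date of first dose of AMG 340". It makes no exception for priming or delay.

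Table 4-1 applies to all cohorts without distinction, and Protocol 6.2.1.1 says: "The MTD will be identified via isotonic regression of pooled escalation cohort data". Priming is already in use: Protocol 2.2.4.3 reports that a grade 3 CRS event in cohort 5 triggered it.

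Table 1-1 footnote k reads: "C1D9 and C1D10 assessments will only be performed if a priming dose has been implemented on C1D8".

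**The concern.** DLT is the endpoint for the MTD/RP2D objective. A 30% target is meaningful only if the rate refers to the same exposure and follow-up at each dose level. Here the dose that defines the cohort is followed for 21 days in some cohorts and 14 in others, and the two rates enter one decision table and one regression. A full-dose toxicity that starts in the third week counts in an unprimed cohort but not in a primed one.

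The SAP also appears to shorten the window further for exactly the subjects whose full dose was late. Footnote k, taken literally, removes the two assessment days that follow the full dose.

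**Working it through.** **Plan's own figures.** I assumed the usual BOIN defaults, φ1 = 0.6φ and φ2 = 1.4φ, which the documents do not state. With φ = 0.30:

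- λe = ln[(1−0.18)/(1−0.30)] / ln[0.30(1−0.18)/(0.18(1−0.30))] = 0.2365
- λd = ln[(1−0.30)/(1−0.42)] / ln[0.42(1−0.30)/(0.30(1−0.42))] = 0.3585

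These agree with the stated 0.236 and 0.358 to within 0.001, and all 20 entries of Table 4-1 reproduce. The boundaries themselves are sound.

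**Days observed after the full dose** (last window day − full-dose day + 1; d = days of delay)

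| Situation | Protocol | SAP 5.1.1 |
|---|---|---|
| Unprimed, full dose Day 1 | 21−1+1 = 21 | 21 |
| Primed, on time, Day 8 | 21−8+1 = 14 | 14 |
| Primed, d = 4 (the protocol's example), Day 12 | 25−12+1 = 14 | 21−12+1 = 10 |
| Primed, d = 7, Day 15 | 28−15+1 = 14 | 21−15+1 = 7 |

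The extension keeps 14 days and never restores 21. If the SAP's 21 days means elapsed days, its window closes on Day 22 and each SAP figure rises by one. The conflict remains.

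**Evaluability.** Protocol 9.3 and SAP 6.3.3 accept a subject who completes the first cycle or has a DLT in it. Neither mentions the extension. It is therefore unclear how to treat a DLT in the extension, or a subject who leaves after Day 21 but before the extension ends.

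**Effect on decisions.** Inputs are a true 21-day rate of 40% (assumed), n = 6, escalation at ≤1 DLT and de-escalation at ≥3 (Table 4-1), and half-lives of 4.16 and 8.57 days (Protocol 2.2.4.3). Priming-dose risk is set to zero.

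If a fraction f of the 21-day cumulative hazard falls in the first 14 days, the 14-day risk is q = 1 − 0.6^f. Constant hazard gives f = 14/21. If hazard follows serum level, f = (1−e^(−14k))/(1−e^(−21k)) with k = ln2/t½. P(escalate) = (1−q)^6 + 6q(1−q)^5, and P(de-escalate) is the binomial probability of 3 or more.

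| Onset assumption | f | q | P(escalate) | P(de-escalate) |
|---|---|---|---|---|
| Full 21 days observed | 1 | 0.400 | 23% | 46% |
| Onset half-life 1–2 days | over 0.99 | 0.398–0.400 | 23–24% | 45–46% |
| Hazard follows 4.16 d | 0.931 | 0.379 | 27% | 41% |
| Hazard follows 8.57 d | 0.830 | 0.345 | 33% | 34% |
| Constant hazard | 0.667 | 0.289 | 45% | 23% |

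**Priming-dose offset.** DLTs in the priming week add to the count. The priming-week risk that brings the total back to 40% is 1 − 0.6/(1−q). For the three lower rows this is 1 − 0.6/0.621 = 3%, 1 − 0.6/0.655 = 8% and 1 − 0.6/0.711 = 16%.

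**Laboratory timing.** The last scheduled cycle 1 draw that is clearly inside the window is Day 15. That is 14 days after an unprimed full dose and 7 days after a primed one. C2D1 is nominally Day 22 with ±1 day. It can fall inside or outside the window, depending on the actual visit day and on how the SAP's 21 days are counted.

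**Footnote k.** Under 6.2.1.2 the priming dose is on Day 1. Under Table 1-1 footnote c and Table 6-1 a second one, if used, is on Day 5. Day 8 is the full dose. Footnotes c, d and j provide admission, extra vital signs and dosing on Day 8 whenever priming is used. The condition in footnote k is therefore never met as worded, and the Day 9 and 10 examination, vital signs, chemistry and hematology would not be triggered.

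**The case against.** The strongest reply is that the window is a deliberate choice. The unit assessed is the cycle 1 regimen, every subject is followed for 21 days, and priming-dose DLTs count. That stands as a description. It also means that the net direction of bias is not established: a modest priming-week risk can cancel the lost days, as the offset shows.

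Protocol 6.2.1.2 names grade ≥3 CRS as the likeliest DLT, and Appendix 10 places raised CRS risk in the first few days after the initial dose. For early events the seven days matter little.

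There are also safeguards. The DLRT may weigh events outside the window. The Medical Monitor, with the investigator, may call other events DLTs (6.2.1.6.1.2). Part A accrual is suspended if more than 33% have unacceptable toxicity, including outside the window (6.2.1.3.1). Appendix 3 requires a unanimous vote to escalate, although 6.2.1.1 speaks of a simple majority. These are real but largely discretionary. Apart from events reclassified as DLTs, none puts a late event into the BOIN count or the regression.

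A reader might infer that every primed window should run to Day 28. On schedule, that span includes the C2D1 full dose. Primed levels would then be judged on two full doses against one, so the documents do not make this the clear remedy.

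On footnote k, the intent can be guessed from footnotes c, d and j. It is probably a slip, but the literal text removes safety assessments.

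**Conclusion.** The difference of 14 against 21 days is a fact of the documents, as is the shared use of Table 4-1 and the pooled regression. Its effect ranges from near nil with early onset to P(escalate) of 45% instead of 23% under constant hazard. Those figures assume a true rate of 40%, six subjects and no priming-dose risk.

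A reader might infer that primed cohorts have been shown to look safer than they are. The documents do not support that, because they give no onset times and priming-dose DLTs count. Nor is the one reported DLT subject, with neutropenia and thrombocytopenia, evidence: onset day, cohort and priming status are not given.

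Two defects do not depend on any assumption. SAP 5.1.1 excludes DLTs that Protocol 6.2.1.2 includes when the full dose is late. Footnote k names a priming dose on a day that never has one. DLRT decisions run under the protocol, so the SAP conflict bears on the reported DLT table, and on the MTD estimate if the regression uses the SAP's count.

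**What to change.** - Reconcile SAP 5.1.1 and the DLT-evaluable definition (Protocol 9.3, SAP 6.3.3) with Protocol 6.2.1.2, so that DLTs in the extended period count in the DLT table and the isotonic regression.
- State whether the C2D1 pre-dose laboratory results fall inside the window, and whether the SAP's 21 days are calendar days including Day 1 or elapsed days.
- Reconcile footnote k with 6.2.1.2 and footnotes c, d and j, so that it refers to a dose given on C1D8.
- Add a supplementary tabulation by dose level of events meeting DLT criteria through 21 days after the first full dose in primed cohorts. Flag those that start after the C2D1 dose, and leave the BOIN count unchanged.

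The cost is wording in both documents and slightly more analysis work. No visits or patients are added.

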##### **6.2.1.4.1.1 Non-hematologic Dose-limiting Toxicity**

- Non-hematological adverse events grade  $\geq 3$  with the following exceptions:
  - Grade 3 or 4 isolated electrolyte abnormalities (ie, those occurring without clinical consequence) that resolve, with or without intervention, to grade  $\leq 1$  within 72 hours.
  - Grade 3 hyperglycemia responsive to optimal medical management within 72 hours.
  - Grade 3 nausea/vomiting/diarrhea responsive to optimal medical management within 72 hours.
  - Alopecia or vitiligo of any grade.
  - Grade 3 fatigue lasting  $< 10$  days.
  - Grade 3 fever (defined as a temperature  $\geq 40^{\circ}\text{C}$  with a duration of  $\leq 24$  hours occurring outside the context of CRS
  - Laboratory parameters of grade 3, not considered clinically relevant, and improved to grade (less than or equal to) 2 within 72 hours, will not be considered DLTs. Laboratory parameters with long half-lives, (ie, ALT, GGT, ALP, and lipase), will likewise not be considered DLTs if they are not considered clinically relevant, and improve to grade  $\leq 2$  within 7 days.
  - Adverse events that require a delay in initiation of the next scheduled cycle by  $> 14$  days.

##### **6.2.1.4.1.2 Hematologic Dose-limiting Toxicity**

- Grade 3 CRS that does not resolve to  $\leq$  grade 1 within 72 hours or grade 4 CRS.
- Grade 3 TLS that does not resolve to  $\leq$  grade 1 within 72 hours or grade 4 TLS.
- Grade 4 neutropenia for  $> 5$  days or febrile neutropenia.
- Grade 3 thrombocytopenia with bleeding or grade 4 thrombocytopenia.
- Grade 4 anemia.
- Grade 5 adverse events.
- Lymphopenia will not be considered a DLT.

- Adverse events that require a delay in initiation of the next scheduled cycle by > 14 days.

#### **6.2.1.5 Echocardiogram/Multigated Acquisition Scan**

Echocardiogram (ECHO) or multigated acquisition (MUGA) will be performed to assess cardiac ejection fraction and will occur at time points specified in the Schedule of Activities (Section 1.3).

ECHO/MUGA should include an evaluation from left ventricular ejection fraction. Additional ECHO/MUGA assessments may be performed as clinically indicated.

#### **6.2.1.6 Specific Guidance for Cytokine Release Syndrome**

Refer to Appendix 10 (Section 11.10) for CRS definitions.

The symptoms associated with the CRS event do not meet the definition of an adverse event as defined in Section 11.4. Therefore, the CRS associated event (ie, CRS, cytokine storm) should be documented on the Event CRF as the diagnosis. However, since it is important to document all symptoms related to a CRS event, a CRS Symptoms eCRF will also be available to record the symptoms associated with each CRS event. If the severity of a CRS event changes from the date of onset to the date of resolution, record a single event for each increased level of severity on the Event CRF and fill out an associated CRS Symptoms eCRF. If the symptoms worsen enough to impact the overall CRS grade, it is important to remember to record a new CRS event on the Event eCRF with the appropriate grade. Temperature may normalize within a few hours of treatment, whereas the other components of CRS take longer to resolve. Once treatments are used to manage the fever, the subject is considered to still have CRS, even in the absence of fever, until all signs and symptoms leading to the diagnosis of CRS have resolved. Likewise, CRS can be downgraded in an afebrile subject treated with anti-cytokine therapy as their hemodynamic status and/or hypoxia improves. Typically, a subject with severe CRS whose fever, oxygen, and pressor requirements have resolved may be assumed to have resolved CRS unless there are alternative causes for the fever, hypoxia, and/or hypotension.

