**Table 2-2. Key Safety Risk for AMG 340**

Safety Risk	Description
Identified Risk	
Cytokine release syndrome (CRS)	Signs and symptoms may include (but not limited to) the following: 

• constitutional – fever, rigors, fatigue, malaise

• neurologic – confusion, headache, mental status changes, dysphasia, tremors, dysmetria, gait abnormalities, seizure (refer to immune-effector cell associated neurologic syndrome [ICANS] guidance in Section 6.2.1.6.1.1)

• respiratory – dyspnea, tachypnea, hypoxemia

• cardiovascular – tachycardia, hypotension

• gastrointestinal – nausea, vomiting, diarrhea

• hepatic – transaminitis, hyperbilirubinemia

• hematology – thrombocytopenia, bleeding, hypofibrinogenemia, elevated D-dimer

• skin – rash

Potential Safety Concerns	
Tumor lysis syndrome	Signs and symptoms may include hyperkalemia, hyperphosphatemia, hyperuricemia, hyperuricosuria, and hypocalcemia, potentially causing lethal cardiac arrhythmias, seizures, and/or renal failure.
Gastrointestinal toxicities	Signs and symptoms may include nausea, vomiting, diarrhea, abdominal pain, gastrointestinal inflammation and ulceration; mostly associated with CRS.
Neurological toxicities	Signs and symptoms include confusional state, headache, dizziness, encephalopathy, tremor, aphasia, and syncope; mostly associated with CRS.

Clinical signs and symptoms of CRS will be continually monitored throughout the duration of the study and at the time points indicated in Schedule of Activities (Section 1.3). Refer to Table 6-6, and Sections 6.1.5, 6.2.1.6.1.1, and 11.10 for specific recommendations regarding the mitigation and management of the risk.

Coronavirus disease 2019 (COVID-19) infection may theoretically increase the signs and symptoms of CRS. Refer to Section 5.2 and section below for additional guidance related to COVID-19.

The key safety risks are described further in the AMG 340 IB.

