**Table 6-2. CRS Grading (ASTCT; Lee et al, 2019)**

CRS Parameter	Grade 1	Grade 2	Grade 3	Grade 4
Fever a	Temperature $\geq 38^{\circ}\text{C}$	Temperature $\geq 38^{\circ}\text{C}$	Temperature $\geq 38^{\circ}\text{C}$	Temperature $\geq 38^{\circ}\text{C}$

		With		
Hypotension	None	Not requiring vasopressors	Requiring a single vasopressor (not including vasopressin)	Requiring multiple vasopressors (not including vasopressin)
		And/or b		
Hypoxia	None	Requiring low-flow oxygen ( $\leq 6$ L/minute) nasal cannula or blow-by	Requiring high-flow nasal cannula ( $> 6$ L/min), facemask, non-rebreather mask, or Venturi mask	Requiring positive pressure (eg, CPAP, BiPAP, intubation and mechanical ventilation)

ASTCT = American Society for Transplantation and Cellular Therapy; BiPAP = bilevel positive airway pressure; CPAP = continuous positive airway pressure; CRS = cytokine release syndrome  
Organ toxicities associated with CRS may be graded according to CTCAE v5.0 but they do not influence CRS grading.

a Fever is defined as temperature  $\geq 38^{\circ}\text{C}$  not attributable to any other cause. In subjects who have CRS then receive antipyretic or anti-cytokine therapy such as tocilizumab or steroids, fever is no longer required to grade subsequent CRS severity. In this case, CRS grading is driven by hypotension and/or hypoxia.  
b CRS grade is determined by the more severe event: hypotension or hypoxia not attributable to any other cause. For example, a subject with temperature of  $39.5^{\circ}\text{C}$ , hypotension requiring 1 vasopressor, and hypoxia requiring low-flow nasal cannula is classified as grade 3 CRS.

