##### **8.4.3 Clinical Laboratory Assessments**

Refer to Section 11.2 for the list of clinical laboratory tests to be performed and to the Schedule of Activities (Section 1.3) for the timing and frequency.

The investigator is responsible for reviewing laboratory test results and recording any clinically relevant changes occurring during the study in the Events CRF. The investigator must determine whether an abnormal value in an individual study subject represents a clinically significant change from the subject's baseline values. In general, abnormal laboratory findings without clinical significance (based on the investigator's judgment) are not to be recorded as adverse events. However, laboratory value changes that require treatment or adjustment in current therapy are considered adverse

events. Where applicable, clinical sequelae (not the laboratory abnormality) are to be recorded as the adverse event.

All protocol-required laboratory assessments, as defined in Section [11.2](#), must be conducted in accordance with the laboratory manual and the Schedule of Activities ([Table 1-1](#)).

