## **11.4 Appendix 4. Safety Events: Definitions and Procedures for Recording, Evaluating, Follow-up and Reporting**

### **Definition of Adverse Event**

Adverse Event Definition

• An adverse event is any untoward medical occurrence in a clinical study subject irrespective of a causal relationship with the study treatment.

• Note: An adverse event can therefore be any unfavorable and unintended sign (including an abnormal laboratory finding), symptom, or disease (new or exacerbated) temporally associated with the use of a treatment, combination product, medical device or procedure.

• Note: Treatment-emergent adverse events will be defined in the Statistical Analysis Plan (SAP).

Events Meeting the Adverse Event Definition

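### Section 6.2.1.6 misstates the adverse event definition for CRS symptoms, so thrombocytopenia, bleeding or an isolated liver-test rise attributed to CRS can go uncounted as a DLT

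*Protocol*

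**What the plan says.** **Recording.** Protocol Section 6.2.1.6 says: "The symptoms associated with the CRS event do not meet the definition of an adverse event as defined in Section 11.4". It then directs that CRS be entered on the Event CRF as the diagnosis and its symptoms on a separate CRS Symptoms eCRF. The section it cites defines an adverse event to include "any unfavorable and unintended sign (including an abnormal laboratory finding), symptom, or disease" arising in time with treatment, and its list of events that fall outside the definition has no CRS item. Section 8.4.3 treats as adverse events "laboratory value changes that require treatment or adjustment in current therapy". Section 11.4 does separately ask for the diagnosis to be recorded in place of its individual signs and symptoms.

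**What counts as a CRS sign.** Table 2-2 includes "hematology – thrombocytopenia, bleeding, hypofibrinogenemia, elevated D-dimer", and lists transaminitis and hyperbilirubinemia as hepatic signs. Appendix 10, to which Section 6.2.1.6 refers for CRS definitions, lists bleeding, transaminitis and hyperbilirubinemia but omits thrombocytopenia.

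**Grading.** Table 6-2 bases the CRS grade on fever, hypotension and hypoxia, and notes: "Organ toxicities associated with CRS may be graded according to CTCAE v5.0 but they do not influence CRS grading".

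**DLTs.** Section 6.2.1.4.1 says: "A DLT is defined as a treatment emergent adverse event that is not unequivocally due to" the malignancy or another outside cause, and that meets listed criteria. These include "Grade 3 thrombocytopenia with bleeding or grade 4 thrombocytopenia" and, with listed exceptions, non-hematologic events of grade 3 or higher. CRS has its own bullet: grade 4, or grade 3 that has not fallen to grade 1 or less within 72 hours. SAP Section 5.1.1 says: "Investigators determine whether a TEAE qualifies as a DLT per the definition described in protocol section 6.2.1.4.1".

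**The concern.** Sections 6.2.1.6 and 11.4 cannot both be right about what an adverse event is, and the protocol does not say which prevails. The consequence goes beyond form completion. DLTs and treatment-emergent adverse events are primary endpoints. The DLT count is the input to the BOIN table, and the MTD is estimated by isotonic regression on the pooled escalation data.

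If a site follows Section 6.2.1.6 literally, an organ toxicity treated as a symptom of CRS is not an adverse event, hence not treatment-emergent, hence not a DLT. It cannot surface through the CRS grade either, because organ toxicity is excluded from that grade. It would also be missing from the adverse event tables, and the SAP names no analysis of the CRS Symptoms eCRF. No sentence in either document says that a toxicity meeting its own DLT criterion must be recorded and counted separately when it accompanies CRS.

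**Working it through.** **1. Follow one case through the text.** Take a subject with fever only, which is grade 1 CRS under Table 6-2, and grade 4 thrombocytopenia.

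| Question | Literal reading of 6.2.1.6 | Reading from 11.4, 8.4.3 and 6.2.1.4.1.2 |
|---|---|---|
| Is the thrombocytopenia an adverse event? | No: a CRS symptom (Table 2-2) | Yes: an abnormal laboratory finding, certainly if it needs treatment |
| What is on the Event CRF? | CRS grade 1 | CRS grade 1 and thrombocytopenia grade 4 |
| Is there a DLT? | No | Yes: it meets its own bullet |

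The same split arises for any CRS that is not itself a DLT: grade 1 or 2, or grade 3 that settles to grade 1 or less within 72 hours. The gap is therefore not confined to low-grade CRS.

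**2. Reproduce the BOIN table.** The target is φ = 0.30 (Section 4.1.1). The usual defaults are assumed: p1 = 0.6φ = 0.18 and p2 = 1.4φ = 0.42.

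- λe = ln[(1−p1)/(1−φ)] / ln[φ(1−p1)/(p1(1−φ))] = ln(0.82/0.70) / ln(0.246/0.126) = 0.2365
- λd = ln[(1−φ)/(1−p2)] / ln[p2(1−φ)/(φ(1−p2))] = ln(0.70/0.58) / ln(0.294/0.174) = 0.3585

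The protocol's 0.236 and 0.358 are these values truncated. Rounding λe·n down and λd·n up reproduces all 20 entries of Table 4-1.

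**3. Remove one DLT.** From Table 4-1:

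| Treated | True DLTs and decision | Decision if one is uncounted |
|---|---|---|
| 3 | 1, stay | escalate |
| 3 | 2, de-escalate | stay |
| 5 | 2, de-escalate | escalate |
| 6 | 2, stay | escalate |
| 6 | 3, de-escalate | stay |

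At every n from 1 to 10 there is at least one count at which losing a single DLT changes the decision.

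**4. Illustrate the size.** The share f of true DLTs that would be lost is not in the documents, so 0% to 50% is an assumed range. The observed rate is q = p(1−f). The probability of an escalate result is (1−q)³ at n = 3 and (1−q)⁶ + 6q(1−q)⁵ at n = 6.

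| n, true DLT rate p | f = 0 | 10% | 25% | 50% |
|---|---|---|---|---|
| 3, 0.30 | 0.343 | 0.389 | 0.465 | 0.614 |
| 3, 0.45 | 0.166 | 0.211 | 0.291 | 0.465 |
| 6, 0.30 | 0.420 | 0.487 | 0.594 | 0.776 |
| 6, 0.45 | 0.164 | 0.226 | 0.343 | 0.594 |

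For example, at n = 3, p = 0.45 and f = 25%: q = 0.3375 and 0.6625³ = 0.291. These figures describe the count rule at a single look, before any judgement by the dose level review team.

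**5. What the data to date show.** Section 2.2.4.3 (cutoff 08 March 2022) reports CRS of any grade in 9 of 23 treated subjects (39.1%), and one subject with DLTs of neutropenia and thrombocytopenia. It does not say whether any organ toxicity coincided with CRS, so it gives no value for f.

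**The case against.** The case for leaving the text alone has real force. Section 6.2.1.6 speaks of symptoms, and a platelet count is a laboratory finding. The sentence can be read as the ordinary practice of recording a diagnosis in place of its symptoms, and it does not mention DLTs. The DLT criteria list CRS and thrombocytopenia as independent bullets with no CRS exemption. Table 6-6 refers thrombocytopenia in CRS to Section 6.2.1.4, which requires laboratory abnormalities to be evaluated and contains the DLT definition. Section 6.2.1.6.1.2 allows discretionary DLTs. Escalation also rests on clinically significant toxicity (Section 6.2.1.1), and Appendix 3 puts laboratory results before the review team.

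A reader might infer that severe neurologic and liver toxicity is lost as well. The documents largely do not support this. ICANS is graded as its own event (Sections 6.2.1.6.1.1 and 8.4.6.1.1; SAP 9.6.2). Concurrent transaminase and bilirubin or INR elevations meeting the Appendix 7 criteria must be reported as serious adverse events and entered on a CRF. What remains exposed is thrombocytopenia, bleeding and isolated liver-test rises.

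It is also fair that thrombocytopenia has already been counted as a DLT. But that report predates Amendment 4 (26 September 2022), which added thrombocytopenia to the CRS signs, so it does not settle current practice. The other safeguards reduce the risk without removing it. They rely on judgement, and they do not put a missing event back into the adverse event tables or the DLT count.

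**Conclusion.** The concern holds as an internal contradiction that can cause a DLT to be missed. It is limited to thrombocytopenia, bleeding and isolated liver-test rises that meet an existing criterion and are attributed to CRS that is not itself a DLT. One missed event can change the Table 4-1 decision, as with 1 of 3 read as 0 of 3.

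Two stronger conclusions are tempting. The first is that the plan excludes these toxicities from the DLT count and that BOIN would escalate past them. Exclusion is only one reading of conflicting text, and escalation needs review and a vote. The second is that the MTD is biased upward. No reported event is shown to have been miscounted, 9 of 23 counts all CRS and not CRS with severe organ toxicity, and the share lost is unknown. The probabilities above are illustrations over an assumed range. They are not estimates for this trial.

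**What to change.** - **Section 6.2.1.6:** delete or correct the sentence saying that CRS symptoms fall outside the adverse event definition. Symptoms can still be captured on the CRS Symptoms eCRF.
- **Add one statement:** a laboratory, hematologic, bleeding or hepatic toxicity accompanying CRS that meets an existing Section 6.2.1.4.1 criterion is recorded as its own adverse event with its own CTCAE grade, and is tested against that criterion. No new threshold is introduced.
- **Reconcile the linked text:** Table 2-2, Section 6.2.1.4.1 and its subsections, Table 6-2, Section 8.4.3, the definition and recording rules in Section 11.4, Appendix 10 and SAP Section 5.1.1.
- **Check existing records:** review the CRS Symptoms eCRFs and laboratory data on this basis at the next dose level review. This is a check and does not presume that an error has occurred.

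The cost is protocol and CRF-completion wording plus one record review. The downside is some double recording with CRS, and DLT and grade 3 or higher rates that may look slightly less favourable.
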